#### PrEP adherence

High adherence is important for PrEP effectiveness in preventing HIV acquisition. Study staff also will provide brief adherence counseling at each scheduled visit, to mimic "real world" counseling. Data on adherence to the product use regimen will be collected via standardized intervieweradministered questions to ascertain product use. PrEP use will be measured by dispensing records, and self-report through a validated 3-item questionnaire. Clinic and pharmacy records will be used to document PrEP prescriptions at the ANC clinics and IDI Kasangati, abstracted in real time from pharmacy records and entered into an electronic database. Adherence will also be assessed through tenofovir drug levels in male partners 3 and 6 months after PrEP initiation.

#### PrEP safety

The Partners PrEP Study demonstrated that PrEP (including FTC/TDF) was safe for use in heterosexual men and women in Uganda. There were no statistically significant differences in the frequency of deaths, serious adverse events, adverse events overall, or key laboratory adverse events for those receiving PrEP compared to those receiving placebo [72].

For the purposes of this study, only serious adverse events (SAEs) and adverse events Grade 3 and above related to PrEP use will be obtained. All AEs that result in a clinical hold or permanent discontinuation of PrEP will be reported on the AE Log CRF regardless of grade.

With appropriate permission of the participant, whenever possible, records from all non-study medical providers related to SAEs will be obtained and required data elements will be recorded on study CRFs. All participants reporting an AE will be followed clinically, until the AE resolves (returns to baseline) or stabilizes.

Reporting on adverse events to relevant IRBs will be according to relevant regulations.

#### Retention

Retention measures for pregnant women and male partners will be those regularly used in previous PrEP studies at the IDI Kasangati – reminder calls, text messages, peer support, and home visits when individuals have several missed visits or an abnormal test result. Couples who break up will remain in the study but have separate clinic visits. We will continue to collect data about sexual behavior and PrEP and ART use. Research procedures for men will include behavioral questionnaires and blood collection to test for tenofovir drug concentration levels among men using PrEP.

#### HIV testing

HIV testing will be performed in accordance with Uganda HIV testing algorithms[73]. Men who are tested through HIVST will receive a voucher for confirmatory testing, either at the ANC where their partner receives care or at IDI Kasangati. HIV testing for men in the invitation letter arm and confirmatory testing for men in the HIVST arm will be accompanied by post-test counseling. All counseling and testing approaches will be in accordance with Uganda HIV counseling and testing guidelines.

#### Procedures for HIV-positive men

Men who are HIV-positive will receive ART adherence support, clinical monitoring and quarterly refills. A baseline CD4 count will be used to screen for risk of opportunistic infections. Treatment will be provided by local HIV care providers or at IDI Kasangati. The recommended first line regimen in Uganda is tenofovir-lamuvidine-efavirenz. Newly initiated partners shall be seen monthly for the first 3 months and quarterly therafter according to national guidelines. At these visits, adherence to ART, drug intolerance, side effects/toxicities and response to ART will be assessed. Viral load monitoring will occur at the 6 month visit (standard of care). Viral load results will be used to support adherence counseling.

#### Follow up study procedures

All data collection will be conducted in a private room in the participant's preferred language, according to the participant's fluency and preference. Women in the intervention and control groups will be asked about their partner's testing and outcome at their PMTCT visits. Women in the intervention arm will be asked to bring the used HIV test strip to the ANC clinic or IDI Kasangati, where confirmatory testing will be offered. Clinic-based confirmatory testing for partners will confirm the accuracy of self-test results and identify false-positive results. Women whose partners have not tested will be encouraged to come with their partners to the ANC clinic or the IDI Kasangati to receive counseling about the importance of HIV testing, PrEP for men who are in HIV serodiscordant partnerships, ART for HIV-positive men, and intimate partner violence, efficacy of ART and PrEP, and her adherence for ART to reduce the risk of maternal-child transmission and sexual transmission. Women in the intervention and control groups whose partners do not come for testing, will be asked whether they discussed HIV testing with their partner, whether their partner was tested elsewhere, the outcome of his test, and whether any social harms resulted.

At each follow up visit, questionnaires will be administered to assess sexual behavior, selfperceived risk, partner testing status, intimate partner violence, relationship power, future fertility desires, self-efficacy, stigma, facilitators and barriers to ART and PrEP (Table 2).

among HIV serodiscordant couples in	1 PMICI B+
Behavioral data	Assessment tool
HIV-positive women	
Facilitators and barriers to ART use	Tool piloted in Partners Demonstration Project and
and adherence in women (Aim 2)	past qualitative and quantitative work[59, 74]
Sexual behavior with study partner and	Tool piloted in multiple couples-based HIV prevention
other partners	services[59, 75]
Internalized stigma	Internalized AIDS-related stigma scale [76]
	Tool piloted in multiple couples-based HIV prevention
Fertility desires	services [59, 75]
Relationship power	Sexual Relationship Power Scale [77]
Intimate partner violence	Conflict Tactics Scale [78, 79]
Alcohol use	Rapid Alcohol Screen [78]
Self-efficacy of ART use	HIV Medication Self-Efficacy Scale [80]
HIV-negative men	
HIV prevention preferences among	Tool piloted in multiple couples-based HV prevention
men (Aim 1)	studies [59, 75]
	Tool piloted in multiple couples-based HIV prevention
Self-perceived risk of HIV	services [59, 75]
Sexual behavior with study partner and	Tool piloted in multiple couples-based HIV prevention
other partners	services [59, 75]
HIV-positive men	
Sexual behavior with study partner and	I ool piloted in multiple couples-based HIV prevention
other partners	services [59, 75]

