In the context of PMTCT B+ programs, HIVST is a promising approach to increasing male partner and couples testing, which has not yet been evaluated. The Kenyan pilot of secondary distribution of HIVST to male partners of pregnant women had encouraging results; however, only a minority (4%) of the 600 women enrolled were HIV-positive and thus more information is needed about how to tailor this approach to HIV-infected women in PMTCT programs. Specific aspects that need to be better understood are HIV-positive pregnant women's willingness and ability to motivate their male partner to test, which may differ from HIV-negative pregnant women, as well as social harms which may be more likely when male partners learn that their partner is HIVpositive. The importance of evaluating HIVST for male partners of women in PMTCT is that their male partners will either be HIV-negative (and thus in an HIV serodiscordant partnership where they could benefit from PrEP or voluntary medical male circumcision) or HIV-positive and need linkage to HIV care and ART. In summary, the feasibility and impact of secondary distribution of HIVST need to be evaluated in PMTCT B+ programs with the expectation that HIV-positive women will require additional counseling and support to broach HIVST with their partners.

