#### Study procedures

#### Specific study procedures are depicted in Figure 3 and detailed in Tables 5-7. Figure 3: Study Procedures for HIV+ Pregnant Women in PMTCT B+

#### Female partner randomization

HIV-positive pregnant women will be randomized in a 2:1 ratio to provision of HIVST kits to use with their male partners or to take an invitation letter to their male partner to be tested at their ANC clinic, or if the male prefers, IDI Kasangati. The 2:1 randomization provides more data on male partner testing with HIVST, which would be useful in assessing uptake, social harms, and

linkage to PrEP and ART. There is ample historical information about male partner testing with invitation letters; the objective of this protocol is to maximize the learning about implementation and outcomes with secondary distribution of HIVST through PMTCT B+.

The randomization code and resulting randomization list will be generated and maintained by the study statistician or designee. A variable size block randomization scheme will be implemented to produce the randomization list and maintained by the study biostatistician. Thus, neither participants nor study staff will be blinded to each participant's randomization group assignment.

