#### Quantitative surveys

A structured interview administered to all HIV-infected female partners at enrollment will ask about knowledge of the partner's HIV status, disclosure, fertility desires, relationship power, and intimate partner violence. At the enrollment visit for male partners, a structured questionnaire will be administered addressing HIV testing history and experience with HIV testing through the PMTCT program. At six months following enrollment, a structured questionnaire will be administered to women and men about acceptability of HIVST and social harms and benefits associated with HIVST and PrEP for male partners. Data will be collected during in person visits, or by phone in accordance with safety guidelines during the COVID-19 pandemic.

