7.4.2. Pregnancy outcomes

Describe pregnancy outcomes by arm, ARV and VS measures during the pregnancy, HIV status of infant.

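### The visit-level question on testing-related social harm goes only to women whose partner has not come for testing, so harm is not ascertained comparably between arms, and the SAP has no by-arm harm table

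*Protocol*

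**What the plan says.** Protocol, Follow up study procedures: women in both arms are asked at their PMTCT visits about the partner's testing and its outcome. A further set of questions has a condition: "Women in the intervention and control groups whose partners do not come for testing, will be asked whether they discussed HIV testing with their partner". It continues with "whether their partner was tested elsewhere, the outcome of his test, and whether any social harms resulted". The same section has intimate partner violence assessed by questionnaire at each follow-up visit, and Table 2 lists a named scale for it.

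Protocol, Quantitative surveys: six months after enrolment, "a structured questionnaire will be administered to women and men about acceptability of HIVST and social harms and benefits associated with HIVST and PrEP". This has no condition on whether the man tested.

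Protocol, Background: the section on self-testing kits says that more needs to be known about "social harms which may be more likely when male partners learn that their partner is HIVpositive". Under Female partner randomization, the 2:1 ratio is justified by more data on self-testing, "which would be useful in assessing uptake, social harms" and linkage.

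SAP: section 7.3.1 treats the man's HIV test at the site as the same thing as his enrolment and makes it the Aim 1a endpoint. The Protocol Summary lets men enrol until 12 months post-partum. Sections 2.2 and 7 contain no social-harm or partner-violence endpoint or table. Section 7.4 does have short descriptive items by arm, such as "Describe pregnancy outcomes by arm, ARV and VS measures during the pregnancy, HIV status of infant".

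**The concern.** The only visit-level item that links harm to testing stops applying once the man comes to the clinic. That is the event the intervention is meant to influence, so the group still being asked is selected after randomisation and is expected to differ between arms. Harm counts from this item cannot be compared by arm as if all randomised women had been asked.

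The Protocol treats social harm as an open question for kits given through HIV-positive women. Its Risks section also names blame and the end of the partnership as possible consequences of couples counselling. Couples who attend for testing are therefore a group in whom harm needs to be asked about. At stake is whether the trial can say, on a randomised basis, how harm compares between kits and letters. The SAP plans no analysis that would attempt this.

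**Working it through.** **Inputs.** 500 women randomised 2:1 (Protocol, Specific Aims): 500 × 2/3 ≈ 333 kit, 500 × 1/3 ≈ 167 letter. Planned test uptake in Protocol Table 3: 20% or 30% letter, 55% or 65% kit (the text above it says 55-66%). SAP Table 1: 20% or 30% letter and 40%, 45% or 50% kit, at one year, although the text of SAP 3.2.1 says 55-65% for the kit arm.

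**Reproducing the plan's own figure.** Overall uptake = (2 × kit + 1 × letter) / 3:
- (2 × 55 + 20) / 3 = 43.3%
- (2 × 55 + 30) / 3 = 46.7%
- (2 × 65 + 20) / 3 = 50.0%
- (2 × 65 + 30) / 3 = 53.3%

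These match the 43, 47, 50 and 53% in Protocol Table 4, so the inputs are being read as the plan uses them. The documents give no figure for ascertainment of social harm.

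**Women to whom the item no longer applies by the end of follow-up.** Assume that coming for testing equals planned uptake. The share is then the arm's uptake.

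| Uptake source | Letter arm (167) | Kit arm (333) | Gap |
|---|---|---|---|
| Protocol Table 3 | 20-30%: 33-50 women | 55-65%: 183-216 women | 55 − 30 = 25 to 65 − 20 = 45 points |
| SAP Table 1 | 20-30%: 33-50 women | 40-50%: 133-167 women | 40 − 30 = 10 to 50 − 20 = 30 points |

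**What the figures bound.** The kit-arm figures are upper limits. A woman whose partner self-tests at home and stays away from the clinic still meets the condition and is asked. In either arm, a woman whose partner comes late may have been asked at earlier visits. The table counts who drops out of one item; it does not count harm that goes unrecorded.

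**Cover from the other instruments.**
- Partner violence questionnaire: every follow-up visit, unconditional. It is not described as linking an event to the offer or the test, or as covering separation or loss of support. The follow-up items are not reproduced in the documents.
- Six-month questionnaire: unconditional, but given once and worded for "social harms and benefits associated with HIVST and PrEP for male partners". The letter is not mentioned. SAP 3.2.1 assumes 1 to 1.5 years of follow-up, which leaves 6 to 12 months after the questionnaire during which men may still come for testing.
- Helpline and in-depth interviews: the first depends on the woman calling, the second covers a selected subsample.

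**The case against.** The strongest case against the point is that the conditional item is not the study's only harm question. The six-month questionnaire covers harms of self-testing whether or not the man tested, and violence is asked about at every visit. On that reading no woman is excluded by design from a self-test harm question because her partner came. This stands, and it rules out the reading that harm after testing is simply missed.

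A reader might also infer that the rule makes kits look safe, or even reverses the comparison. The documents do not support that. The six-month wording names self-testing and PrEP but not the letter, which could under-count harm in the letter arm and so push the other way. The documents give no harm risks by testing status, so any numerical reversal would rest on invented risks and would treat the conditional item as the sole instrument.

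Two further objections have some force. The Background sentence concerns men learning the woman's status, which is disclosure rather than testing; the SAP models the two separately, and a woman who has disclosed but whose partner stays away is still asked. Also, SAP section 1 limits the plan to Aims 1 and 2 and selected secondary objectives, and the Protocol groups social harms with the acceptability work. That explains the missing table but does not supply one, and harm is among the Protocol's stated reasons for the allocation ratio.

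Finally, SAP 4.1 does not say what the monitoring committee reviews, so nothing can be concluded about the counts it sees.

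**Conclusion.** The point holds as a matter of comparability. The visit-level item on testing-related harm depends on a post-randomisation event that is also the Aim 1a endpoint. By the end of follow-up it would no longer apply to at most 55-65% of kit-arm women (40-50% on SAP Table 1) against 20-30% of letter-arm women, assuming that coming for testing equals planned uptake. Violence screening at each visit and the single six-month questionnaire give partial cover, but they do not make testing-related harm comparable between arms. The net direction of any bias cannot be determined from the documents. Separately, the SAP has no by-arm table of social harm or partner violence. This is an inexpensive improvement to the harm assessment; it does not touch the analyses of testing, PrEP/ART uptake or viral suppression.

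**What to change.** 1. Protocol, Follow up study procedures: put the same social-harm item to all women in both arms at every follow-up visit, whether or not the partner came for testing.
2. Protocol, Quantitative surveys: reword the six-month questionnaire so that it is arm-neutral and covers harm following the kit, the letter or the man's test.
3. SAP 7.4: add a by-arm table over all randomised women showing new partner violence and any social harm after enrolment, with the risk difference and 95% confidence interval, and give it to the monitoring committee at its reviews.

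The cost is one existing item asked of more women, one wording change and one extra table. The reported harm rate may rise slightly because more women are asked.

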## Table 2. Data collection to longitudinally assess behavioral factors related to PrEP and ART use

#### HIV seroconversion

Study staff will counsel male partners who seroconvert on PrEP and refer them to local HIV care

providers for ongoing-care and initiation of antiretroviral therapy according to Uganda treatment guidelines. Seroconverters will be asked to remain in the study until completion of the follow up period in order to implement data collection relevant to secondary outcomes -- antiretroviral resistance, plasma viral load and CD4 after HIV seroconversion.

#### Final study visit

Women and male partners will be followed for 12 months post-partum. At 12 months post-partum or when a participant discontinues study participation, they will have a final study visit. Study procedures at this visit will be similar to other follow up visits. All study participants on ART will continue receiving care at a public health clinic of their choice. Participants on PrEP will be referred for care if PrEP becomes available through the public health system.

#### Quantitative surveys

A structured interview administered to all HIV-infected female partners at enrollment will ask about knowledge of the partner's HIV status, disclosure, fertility desires, relationship power, and intimate partner violence. At the enrollment visit for male partners, a structured questionnaire will be administered addressing HIV testing history and experience with HIV testing through the PMTCT program. At six months following enrollment, a structured questionnaire will be administered to women and men about acceptability of HIVST and social harms and benefits associated with HIVST and PrEP for male partners. Data will be collected during in person visits, or by phone in accordance with safety guidelines during the COVID-19 pandemic.

#### Data quality and management

Health information about the mother and child during pregnancy, delivery and after delivery will be documented. Clinic and pharmacy records will be used to document PrEP prescriptions, abstracted in real time from pharmacy records to tablet-based case report forms and entered into an electronic database. Automated legal range checks will be programmed to reduce data entry errors and internal quality control reports will be run monthly. Our team has experience using this data capture method in other studies of HIV prevention.

#### Qualitative data collection

Qualitative data collection will consist of individual in-depth interviews (IDIs), field observations, and focus group discussions (FGDs).

#### IDIs

The qualitative sample of study participants will be stratified by study arm. Specifically, we will carry out 1) up to 50 interviews with male partners 2) up to 60 interviews with pregnant women and 3) PMTCT and HIV providers (up to 10). For interviews with men and women, we will oversample those who are in the intervention arm.

Individual in-depth interviews will be conducted with individuals in the qualitative subsample to

elicit data on acceptability of HIV self-testing and PrEP for male partners (and on the control condition). Some participants may be asked to complete a second in-depth interview, to assess their experience in the study over time. Interviews will be "minimally structured", i.e. guided by topics (rather than pre-designated, open-ended questions) tailored to each group. Examples of topics for interviews with male partners are:

- a) History of HIV testing;
- b) History of relationship with his partner in PMTCT B+;
- c) Response to receiving an HIVST or letter of invitation to test;
- d) Response to the offer of PrEP for prevention (for individuals with negative test results).

Examples of topics to be covered in the interviews with women in PMTCT B+ are:

1) The "story" of providing the HIV self-testing kit or the letter of invitation to test to their partner

- 2) Description of the partner's response
- 3) Partner follow-up in terms of confirmatory HIV testing and/or PrEP
- 4) Impact on the relationship (including social harms)
- 5) Impact on feelings about ART use post-partum

Examples of topics to be covered in the interviews with PMTCT providers are:

1) Perceptions of influences on male partner testing in the context of PMTCT B+;

2) Experiences of implementing male partner testing in the context of PMTCT B+;

3) Perceived responses of male partners to self-testing, and the reasons behind these responses;

4) Perceived responses to the offer of PrEP for male partners who test negative;

5) Patterns of and influences on ART adherence for pregnant women during pregnancy and postpartum;

6) Perceived impact of HIV testing and subsequent initiation of PrEP or ART by male partners on ART adherence for pregnant and post-partum women; and

7) Perspectives on how to facilitate disclosure and minimize social harms in these couples.

During in-depth interviews with PMTCT providers, male partners and women, we may explore the perceptions of COVID-19 and the intersections on status disclosure, male partner testing, and adherence to HIV prevention and treatment during the pandemic.

Interview procedures: In-depth interviews will be conducted by gender-matched Ugandan research assistants (RA). The RA's have been trained in methods of qualitative interviewing by [name], who heads the qualitative team with [name]. Interviews will usually be scheduled 1–3 months following provision of the HIVST kit or letter of invitation to test, but may take place at a later time during study participation. They will be conducted where conversations cannot be overheard. Interviews will be conducted in the interviewee's language of preference (English or Luganda). Provider interviews will be conducted in English. Interviews will be audio-recorded with permission. Participation will be recognized with a small reimbursement, based on local standards. Compensation for travel to the interview will be provided where appropriate.

Producing the interview data: The interview data for this study will consist of up to 120 written transcripts. Immediately following each interview session, the interviewer will produce an exact electronic write-up of the interview in English, using audio-recording and notes taken during the interview as guides. We have developed this approach of direct transcription into English from local languages over many years of qualitative research in Africa and find it produces an accurate transcript while also saving time and resources. We will use Express Scribe, an audio-recording

transcription computer software program, which facilitates transcription.

